7.12.3. Deaths, Other Serious Adverse Events, and Other Notable Adverse Events

TEAEs by PT will be reported.

The general summary of AEs is described in the CPMP SAP Version 5. Other AEs include

- Abuse liability and withdrawal potential following the most recent Lilly Guidance for Assessment of Abuse Potential during Clinical Development.
- Seizures FMQ both narrow and broad terms will be analyzed.

7.12.4. Neurological Exam

In this ISA, neurological exam results will be reported for the entire 10-week study period. Study BP05 will consider the following analyses for the Neurological Exam, which evaluates 6 items and will be summarized by normal/abnormal percentage by item. In addition, we will summarize shift tables for each item in the Neurological Exam.

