***Toxicology Studies and NOAEL Exposure***

Based on the observed convulsion in the 3-month dog toxicology study (reported in 1 dog) as well as convulsion noted in the rat in vivo micronucleus study (reported in 1 rat), a 10-fold exposure multiple based on the observed AUC and Cmax associated with the NOEL for convulsions in dog (the most sensitive species) will be maintained in this **CCI** [REDACTED]

In addition, neurological examination will be conducted at regular intervals during the study period and AEs related to CNS signs and symptoms will be collected during the study. Participants with a history of seizures will be excluded from the study.

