7.1. General Considerations

The estimand for the primary clinical question of interest has been described in the CPMP SAP Version 5.

Unless otherwise specified, efficacy and safety analyses will be conducted for the 8-week double-blind period and separately for the entire 10-week study period.

Other general considerations for analyses are described in the CPMP SAP Version 5.

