7.12.2. Adverse Events

The general analysis of AEs has been described in the CPMP SAP Version 5.

This ISA will report TEAEs separately for the entire 8-week double-blind period, the 2-week post-treatment period, and the entire 10-week study. For TEAEs in the double-blind period, the baseline will be prior to first dose date.

A PTEAE is defined as an event that first occurs or worsens in severity after double-blind treatment phase (after Visit 7) and on or before study discontinuation. This ISA will report PTEAEs for the post-treatment period, as they are important for assessing withdrawal or abuse liability potential. The MedDRA LLT will be used in the post-treatment-emergent computation. The maximum severity for each LLT during the double-blind treatment period (Visits 3 through 7) will be used as a reference.

The baseline of PTEAE is from the first dosing date to Visit 7. The post-treatment phase will be included as postbaseline for this analysis. While unusual, it is possible to have a missing severity for events. **CCI**

CCI

CCI

and PTEAEs will be determined by comparing with treatment period.

PTEAEs will be summarized by PT and by PT within SOC in participants who received LY3857210.

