7.12.5. Clinical Laboratory Evaluation

The general analysis of laboratory parameters is described in the CPMP SAP Version 5.

In this ISA, laboratory results will be reported for the entire 10-week study period. Study BP05 will also consider the following analyses of lab analytes used to assess renal function. The planned summaries for these analytes are the same as those that have been described in the Study

CPMP SAP Version 5; however, the reporting of these analytes will be separate from the general analysis of laboratory parameters.

- Renal data analyses:
 - Serum creatinine (change from baseline in mg/dL)
 - eGFR; Chronic Kidney Disease Epidemiology Collaboration algorithm using serum creatinine) Algorithm: Provided by central laboratory
 - For eGFR calculation, we will summarize shift tables of eGFR changes for baseline versus postbaseline by minimum, maximum, and last observed eGFR result:
 - Category 1: Normal or increase in GFR (≥ 90 mL/min/1.73m²)
 - Category 2: Mild reduction in GFR (60 to 89 mL/min/1.73m²)
 - Category 3a: Moderate (a) reduction in GFR (45 to 59 mL/min/1.73m²)
 - Category 3b: Moderate (b) reduction in GFR (30 to 44 mL/min/1.73m²)
 - Category 4: Severe reduction in GFR (15 to 29 mL/min/1.73m²)
 - Category 5: Kidney failure (GFR <15 mL/min/1.73m² or dialysis).

Abnormal eGFR is specified below and will be summarized in the laboratory summary tables.

- Abnormal low: < 90 mL/min/1.73m²
- Abnormal high: As specified by central laboratory.

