7.12.7. Electrocardiograms

The analysis of ECG parameters is described in the CPMP SAP Version 5. ECG will be reported separately for the 8-week treatment period and the entire 10-week study period.

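### SAP 7.12.4 names only the 10-week period for the neurological exam; add the 8-week on-treatment summary that SAP 7.1 sets as the default

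*SAP*

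**What the plan says.** SAP 7.1 sets the general rule: "Unless otherwise specified, efficacy and safety analyses will be conducted for the 8-week double-blind period and separately for the entire 10-week study period".

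SAP 7.12.4 then says of the neurological exam: "In this ISA, neurological exam results will be reported for the entire 10-week study period". It plans normal/abnormal percentages and shift tables for each item. It does not say whether these are by visit, or which post-baseline value the shifts use.

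SAP 7.12.5 has a parallel sentence: "In this ISA, laboratory results will be reported for the entire 10-week study period". Its eGFR shift tables compare "baseline versus postbaseline by minimum, maximum, and last observed eGFR result".

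The neighbouring sections differ. SAP 7.12.7 states "ECG will be reported separately for the 8-week treatment period and the entire 10-week study period", and 7.12.6 (vital signs) and 7.12.8 (suicidality) follow the same pattern. SAP 7.12.2 splits treatment-emergent adverse events (TEAEs) into the 8-week, 2-week post-treatment and 10-week periods. It reports post-treatment-emergent events "as they are important for assessing withdrawal or abuse liability potential".

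Protocol 2.3.1, after describing convulsions in one dog and one rat, says that "neurological examination will be conducted at regular intervals during the study period". SAP 7.18 lists a treatment-emergent shift on the overall neurologic assessment among its key safety events and gives no window for it.

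**The concern.** The 10-week period includes Visit 801, which Protocol 4.1 places about two weeks after Visit 7 or early discontinuation (ED). An abnormal finding at Visit 801 may reflect withdrawal, or simply background. One during Weeks 2 to 8 is on drug. The SAP treats these as different questions for adverse events but names one combined window for the exam that was added because of the convulsion findings.

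At stake is how the neurological tables can be read. An on-drug effect is diluted by an off-drug visit, and a withdrawal finding could be counted as if it arose on drug. The neurologic shift in 7.18 could take on the same ambiguity.

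**Working it through.** The plan states no figure on this point, so there is none to reproduce. The check compares the reporting windows, counts visits, and then sizes the effect under assumed rates.

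**1. Windows side by side**

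| Safety domain | SAP section | Window named |
|---|---|---|
| Default | 7.1 | 8 weeks and, separately, 10 weeks |
| TEAEs | 7.12.2 | 8 weeks, 2 weeks post-treatment, 10 weeks |
| Neurological exam | 7.12.4 | 10 weeks |
| Laboratory | 7.12.5 | 10 weeks |
| Vital signs | 7.12.6 | 8 weeks and 10 weeks |
| ECG | 7.12.7 | 8 weeks and 10 weeks |
| Suicidality | 7.12.8 | 8 weeks and 10 weeks |
| Neurologic and eGFR shifts as key safety events | 7.18 | none stated |

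Sections 7.12.4 and 7.12.5 do not expressly cancel the default. But a sentence naming one period is not needed if the default applies, and the neighbouring sections take care to name both. The natural reading is that these two are exceptions.

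**2. Visit count**

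The Schedule of Activities in Protocol 1.3 marks the neurological assessment at Visits 3 (baseline), 4, 5, 6, 7, ED and 801. A completer has four post-baseline exams in the treatment period (Visits 4 to 7) and one afterwards (Visit 801), so 1/5 = 20% are off drug. A participant with Visit 4, ED and Visit 801 has 1/3.

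**3. Size, under assumed rates**

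Let p be the background chance of an abnormal exam and q the chance on active drug, with exams independent and a drug effect present only on drug. All rates are assumptions; the documents give none.

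*All exams pooled.* The active-arm percentage over 10 weeks is (4q + p)/5, so the excess over placebo is (4q + p)/5 − p = 0.8(q − p), a loss of one fifth. With p = 2% and q = 5%, it falls from 3.0 to 2.4 points. With p = 5% and q = 10%, it falls from 5.0 to 4.0.

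*Any abnormal exam per participant.*
- Placebo: 1 − (1 − p)^4 over 8 weeks; 1 − (1 − p)^5 over 10 weeks.
- Active: 1 − (1 − q)^4 over 8 weeks; 1 − (1 − q)^4(1 − p) over 10 weeks.

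| p, q | Placebo 8 → 10 wk | Active 8 → 10 wk | Risk ratio | Risk difference (points) |
|---|---|---|---|---|
| 1%, 3% | 3.9% → 4.9% | 11.5% → 12.4% | 2.91 → 2.52 | 7.5 → 7.5 |
| 2%, 5% | 7.8% → 9.6% | 18.5% → 20.2% | 2.39 → 2.10 | 10.8 → 10.6 |
| 5%, 10% | 18.5% → 22.6% | 34.4% → 37.7% | 1.85 → 1.67 | 15.8 → 15.0 |

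The risk difference is multiplied by (1 − p), so it barely moves. The risk ratio falls more.

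**4. Laboratory results**

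Of the three eGFR shifts, the minimum and maximum over 10 weeks still take in every on-drug value. Only the last-observed shift could be replaced by an off-drug value, and only if chemistry is drawn at Visit 801. In the available text, the chemistry row shows Visits 4 to 7 plus one further mark that lines up with ED rather than Visit 801. The table layout is damaged and the master schedule is not available, so this cannot be confirmed.

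**The case against.** The strongest reply is that nothing is lost. The 10-week window contains every on-drug exam, by-visit tables would keep Visit 801 separate, and the general safety methods are in the CPMP SAP, which is not available here. The 7.1 default may also still apply, since 7.12.4 does not say it is overridden. All of this is fair. It makes the defect one of specification rather than data, and mixing follows only if the tables are not by visit. It does not remove the need for the edit: 7.12.4 should itself say which reading is meant.

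Three stronger readings are tempting, and the documents do not support them.

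- A reader might infer that the convulsion analysis itself blurs on-drug and off-drug events. It does not. Seizures are analysed as adverse events through the FDA Medical Query (SAP 7.12.3), TEAEs are split by period, and post-treatment-emergent events are judged against on-treatment severity (7.12.2). The exam supports that monitoring.
- A reader might infer that a neurological abnormality that resolves after stopping would vanish from a last-value shift. Section 7.12.4 contains no last-value rule; that rule appears only for eGFR, where the minimum shift keeps every on-drug decline.
- A reader might infer that eGFR belongs to the drug's main safety concern. Nothing visible says so; the named event of special interest is convulsion (Protocol 8.3.3).

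**Conclusion.** The point holds as an inconsistency with a simple remedy. SAP 7.12.4 departs from the SAP's own default and from its treatment of vital signs, ECG and suicidality, in a domain where the SAP itself takes withdrawal seriously. For a completer, one exam in five is off drug. If the tables pool visits, an effect confined to treatment is diluted by one fifth in the percentage of abnormal exams. Counted per participant, the risk ratio drops moderately and the risk difference hardly changes. These sizes rest on assumed rates, independent exams and no off-drug effect.

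For laboratory results, the case is consistency of wording. A practical effect on the last-observed eGFR shift depends on a Visit 801 chemistry draw that the documents do not show. This is an improvement worth making because it costs almost nothing, not a threat to the safety conclusions.

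**What to change.** - **SAP 7.12.4:** report item percentages and shift tables for the 8-week treatment period, using post-baseline values through Visit 7 or ED, and separately for the 10-week period. State whether tables are by visit and which post-baseline value the shifts use. Show Visit 801 as a post-treatment shift.
- **SAP 7.18:** state that the treatment-emergent neurologic shift uses the 8-week window.
- **SAP 7.12.5:** use the same two-period wording for laboratory results, and define the last-observed eGFR in the 8-week summary as the last on-treatment value.

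The cost is a few sentences of SAP text and one further run of the same tables with a period filter. No assessment, visit or data collection changes.

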7.12.5. Clinical Laboratory Evaluation

The general analysis of laboratory parameters is described in the CPMP SAP Version 5.

In this ISA, laboratory results will be reported for the entire 10-week study period. Study BP05 will also consider the following analyses of lab analytes used to assess renal function. The planned summaries for these analytes are the same as those that have been described in the Study

CPMP SAP Version 5; however, the reporting of these analytes will be separate from the general analysis of laboratory parameters.

- Renal data analyses:
 - Serum creatinine (change from baseline in mg/dL)
 - eGFR; Chronic Kidney Disease Epidemiology Collaboration algorithm using serum creatinine) Algorithm: Provided by central laboratory
 - For eGFR calculation, we will summarize shift tables of eGFR changes for baseline versus postbaseline by minimum, maximum, and last observed eGFR result:
 - Category 1: Normal or increase in GFR (≥ 90 mL/min/1.73m²)
 - Category 2: Mild reduction in GFR (60 to 89 mL/min/1.73m²)
 - Category 3a: Moderate (a) reduction in GFR (45 to 59 mL/min/1.73m²)
 - Category 3b: Moderate (b) reduction in GFR (30 to 44 mL/min/1.73m²)
 - Category 4: Severe reduction in GFR (15 to 29 mL/min/1.73m²)
 - Category 5: Kidney failure (GFR <15 mL/min/1.73m² or dialysis).

Abnormal eGFR is specified below and will be summarized in the laboratory summary tables.

- Abnormal low: < 90 mL/min/1.73m²
- Abnormal high: As specified by central laboratory.

7.12.6. Vital Signs and Other Physical Findings

The analysis of vital sign parameters is described in the CPMP SAP Version 5.

Vital signs will be reported separately for the 8-week treatment period and the entire 10-week study period.

7.12.7. Electrocardiograms

The analysis of ECG parameters is described in the CPMP SAP Version 5. ECG will be reported separately for the 8-week treatment period and the entire 10-week study period.

7.12.8. Suicidal Ideation or Behavior

Reporting of suicidal ideation/behavior through the Columbia Suicide-Severity Rating Scale has been described in the CPMP SAP Version 5. Suicidal ideation/behavior will be reported separately for the 8-week treatment period and the entire 10-week study period.

7.13. Subgroup Analyses

General subgroup analyses are described in the CPMP SAP Version 5.

Subgroup analyses considered for the primary outcome are shown in [Table BP05.7.3](#).

Table BP05.7.3. Subgroup Analyses for Primary Outcome

Subgroup Variable	Categories
Neuropathic pain	Categories: Positive presence (painDETECT total score ≥ 19) Unclear or negative (painDETECT total score < 19)

The subgroup analyses will be conducted using similar modeling approaches as the primary analysis. Additional factors in the model are described in the CPMP SAP Version 5. The treatment difference at the endpoint will be reported within each level of the subgroup factor along with 95% credible intervals. Frequentist MMRM may be performed as a sensitivity analysis using the modeling approach described in the CPMP SAP Version 5.

7.14. Protocol Deviations

Participants with study important protocol deviations will be summarized by type of deviation and listed by treatment and investigative site.

[figure not shown]
Important protocol deviations for the study are described in the CPMP and Study BP05 Trial Issue Management Plans.

7.15. Interim Analyses and Data Monitoring

Safety review will be conducted under the auspices of an Assessment Committee according to the specifications set forth in the protocol. These analyses will be at the CPMP level and will consider data from all ongoing ISAs. Details are provided in the CPMP SAP Version 5. No interim analyses are planned for Study BP05. Unplanned interim analyses may be conducted for reasons including futility analyses, early efficacy analyses, safety analyses, or other analyses, if deemed needed for key business decisions and planning.

7.16. Planned Exploratory Analyses

The following analyses may be conducted for exploratory purposes:

7.17. Totality of Evidence for Efficacy

The totality of evidence analysis approach for efficacy data has been briefly described in the CPMP SAP Version 5. A multivariate Bayesian model will be fit within each ISA to assess efficacy ToE across domains. To inform the aggregation of model-based estimates for domain scores, important weights for each scale within a domain are described in [Table BP05.7.4](#).

7.18. Totality of Evidence for Safety

The totality of evidence analysis approach for safety data has been briefly described in the CPMP SAP Version 5. The key safety events to be considered for Study BP05 are listed below by domain:

General Adverse Event Information

- Serious AEs including death related to study treatment
- Study discontinuation due to AE
- Treatment discontinuation due to AE.

Cardiovascular

- QTcF prolongation: >60 msec increase or QTcF >500 msec
- Serious cardiac disorders AE.

Liver function

- Drug-induced liver injury: at least 1 of the following 2 conditions:

Metabolic function

- Serious hypoglycemia AE
- Serious hyperglycemia AE
- Treatment-emergent hemoglobin A1c: Shift from low/normal at baseline to high at least once.

Renal function

- Treatment-emergent abnormal eGFR: Shifts
 - Mild at baseline to moderate/severe
 - Moderate at baseline to severe.

Neurologic function

- Treatment-emergent abnormal shift on the overall neurologic assessment
- Serious neurologic events
- Seizures FMQ both narrow and broad terms.

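### The renal key safety event in SAP 7.18 lists no shift from a normal baseline eGFR, so a participant starting at 90 or above cannot have it

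*SAP*

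**What the plan says.** SAP 7.18 introduces its list with "The key safety events to be considered for Study BP05 are listed below by domain". The renal domain has one entry, treatment-emergent abnormal eGFR, made up of two shifts: "Mild at baseline to moderate/severe" and "Moderate at baseline to severe". The section gives no cut-offs for these terms.

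SAP 7.12.5 gives the only eGFR categories in the documents. It starts with "Category 1: Normal or increase in GFR", set at 90 mL/min/1.73 m² or more, followed by "Category 2: Mild reduction in GFR (60 to 89" mL/min/1.73 m²). Moderate is split into 3a (45 to 59) and 3b (30 to 44). Category 4, severe, is 15 to 29, and Category 5, kidney failure, is below 15 or dialysis. The same section sets abnormal low at below 90 and plans shift tables by minimum, maximum and last postbaseline value.

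Protocol 5.2 excludes an eGFR below 30 at Visit 1 or Visit 2 and sets no upper limit, so participants with a normal baseline can enrol.

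**The concern.** With abnormal low at below 90, both listed starting states are already abnormal. The event therefore captures worsening of existing impairment but never a change from normal to abnormal, which its label would lead a reader to expect. The HbA1c event in the same list works the other way: "Shift from low/normal at baseline to high at least once".

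A renal count built on this rule leaves out falls from normal to moderate, severe or kidney failure, while counting moderate and severe end states reached from a mild baseline. The cardiovascular, metabolic and neurologic domains each also list serious adverse events. The renal domain does not, so a participant starting at 90 or above cannot contribute to it at all. The wording also leaves open whether severe takes in Category 5.

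**Working it through.** The plan states no figure to reproduce. The check applies the two 7.18 shifts to every worsening shift that the 7.12.5 categories allow.

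**Inputs.** Categories come from SAP 7.12.5, listed shifts from SAP 7.18, and the entry limit of eGFR below 30 from Protocol 5.2. The analysis baseline is assumed to respect that limit, so the possible baselines are normal, mild and moderate. Categories 3a and 3b are merged first, because 7.18 says only moderate.

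| Baseline | Worse end states | Possible | Counted as written | Counted if severe includes Category 5 |
|---|---|---|---|---|
| Normal | mild, moderate, severe, failure | 4 | 0 | 0 |
| Mild | moderate, severe, failure | 3 | 2 | 3 |
| Moderate | severe, failure | 2 | 1 | 2 |
| Total | | 9 | 3 | 5 |

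**With 3a and 3b kept apart.** Possible shifts: 5 + 4 + 3 + 2 = 14. As written, the rule counts 2→3a, 2→3b, 2→4, 3a→4 and 3b→4, which is 5. Including Category 5 adds 2→5, 3a→5 and 3b→5, which gives 8. From normal the count is 0 of 5 either way.

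**All values.** Checking each whole-number baseline from 90 to 150 against each postbaseline value from 0 to 150 finds no pair that meets the event.

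**Same end value, different baseline.** Percentage fall = (baseline − end) / baseline.

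- 89 to 29: 60/89 = 67.4%, counted.
- 90 to 29: 61/90 = 67.8%, not counted.
- 85 to 25: 60/85 = 70.6%, counted.
- 95 to 25: 70/95 = 73.7%, not counted.

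In whole-number values, 90 to 29 is the smallest possible fall from normal to severe. Every such fall is therefore at least 67.8%, and none is counted. By contrast, 62 to 58 (4/62 = 6.5%) is counted.

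These are counts of category pairs. They are not participants or probabilities.

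**The case against.** The strongest objection is that the list may be incomplete. The liver entry in the same section announces "at least 1 of the following 2 conditions" and then shows neither, so text has been lost nearby. A line starting from normal would naturally stand first, and its loss would leave what is seen here. This cannot be ruled out. However, the liver entry visibly breaks off after a colon, whereas the renal entry shows no gap and ends in a full stop.

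Second, "The totality of evidence analysis approach for safety data has been briefly described in the CPMP SAP Version 5", and that document was not available. 7.18 also does not cite the 7.12.5 cut-offs, so using them is an inference from shared words. Both points stand as limits. Still, the events for this study are listed in 7.18 itself, and no other eGFR categories are supplied.

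Third, falls from normal remain visible in the 7.12.5 shift tables, the creatinine change and the abnormal-low summary. Related serious events, or events leading to discontinuation, could enter under the general adverse event domain. The supplied text ties no decision rule to the list. All of this is correct, and it limits the consequence to the 7.18 renal count.

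Fourth, restricting the event to worsening of existing impairment may be deliberate. Worsening does fit one half of the SAP's definition of a treatment-emergent adverse event. But the SAP gives no such reason, and the objection does not explain why 89 to 29 should count when 90 to 29 does not.

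**Conclusion.** The concern holds and should be fixed, with medium confidence. On the 7.12.5 categories, the 7.18 renal event counts none of the shifts from a normal baseline and only 3 or 5 of the 9 worsening shifts overall. The conclusion assumes that the 7.18 terms carry their 7.12.5 meanings, that the renal list is complete as shown, and that CPMP SAP Version 5 adds no shift from normal. The error would affect one entry in the safety totality-of-evidence list. No efficacy result depends on it, and these falls would still be reported elsewhere.

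**What to change.** Before unblinding, amend the renal event in SAP 7.18 as follows:

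1. Tie its terms to the 7.12.5 categories.
2. Add shifts from normal (Category 1) to moderate, severe or kidney failure.
3. State that severe includes Category 5.
4. Base the event on the minimum postbaseline eGFR, which 7.12.5 already plans to tabulate. 7.18 does not say which postbaseline value applies.

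Also state that normal-to-mild and 3a-to-3b shifts are shown only in the 7.12.5 tables. The amended rule counts 3 + 3 + 2 = 8 of the 9 merged shifts, leaving out normal to mild. With 3a and 3b apart it counts 12 of 14, leaving out 1→2 and 3a→3b.

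It remains a category rule: 95 to 61 (34/95 = 35.8%) stays outside the event and 60 to 59 (1/60 = 1.7%) inside it. What it gains is that a moderate or worse end state counts alike from normal and mild baselines.

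If leaving out normal baselines is intended, or CPMP SAP Version 5 already covers them, a sentence in 7.18 saying so would be enough on that point.

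The cost is a few lines of SAP wording and minor programming, with no new data. The renal event count may become less favourable.
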